9. STATISTICAL CONSIDERATIONS

9.1 Statistical Hypotheses

Overall study design is described in Section 4.1 of the protocol. Subjects who are hospitalized for COVID-19 symptoms and meet the eligibility criteria will be randomized 1:1 to receive acalabrutinib plus BSC (Arm 1: n=30) vs BSC (Arm 2: n=30).

Stratification by age (≥ 65 vs < 65 years) and comorbidities (present vs absent) will be applied to randomization.

The primary objective of the study is to evaluate the safety and preliminary efficacy of acalabrutinib plus BSC (Arm 1) vs BSC (Arm 2). There is no formal hypothesis testing for the safety and efficacy endpoints. The primary focus for the efficacy is to estimate the treatment effect as measured by the difference between treatment arms in the proportion of subjects who are alive and free of respiratory failure.

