9.2 Sample Size Determination

The planned total number of subjects in this study is 60.

Based on the reported rate of deaths and need for ICU admission (a surrogate for respiratory failure) in subjects who are hospitalized for COVID-19 (Arentz et al 2020, Bhatraju et al 2020, CDC 2020, Grasselli et al 2020), it assumed that the proportion of subjects who are alive and free of respiratory failure at Day 28 is 70% under BSC. A targeted difference of 20% between two treatment arms (ie, 90% for acalabrutinib + BSC) is of clinical interest. With a total sample size of 60, the half-width of the 2-sided 90% confidence interval for the observed treatment difference is 16.4% using unpooled estimate for variance. It has approximately 64% power, with a 2-sided type I error of 0.1, to detect a difference of 20% between the 2 arms.

9.3 **Populations for Analyses**

The analysis populations are defined as shown in Table 6.

Population/ Analysis set	Description	
Full analysis set (ITT population)	The full analysis set will include all subjects who are randomized and will be used for all efficacy analyses. Treatment arms will be compared on the basis of randomized study treatment, regardless of the treatment actually received. Subjects who were randomized but did not subsequently go on to receive study treatment will be included in the analysis in the treatment arm to which they were randomized, following the "intent-to-treat" principle.	
Per-protocol analysis set	The per-protocol analysis set will be a subset of the ITT population including only subjects without important detected protocol deviations affecting the efficacy endpoints. Subjects will be summarized according to the actual treatment first received. The primary endpoint of the study will also be summarized for this population.	

Table 6Analysis Populations

Population/ Analysis set	Description
Safety analysis set	The safety analysis set (Safety population) is based on the treatment subjects actually received. In this study, the treatment is either acalabrutinib + BSC or BSC only. If a subject receives at least 1 dose of acalabrutinib, the subject is considered as acalabrutinib-treated, regardless which arm the subject was randomized to. Subjects who are randomized to acalabrutinib + BSC but do not receive any acalabrutinib will be summarized in the BSC group.

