3.1.15 Relative change from baseline in oxygenation index

This is defined as the percentage change from baseline in oxygenation index (SpO_2/FiO_2) to Days 3, 5, 7 and 10. For this endpoint, baseline is defined as the observation on the date of randomization (Day 1) only.

Oxygenation index is calculated as

$$SpO_2 [\%] / FiO_2 [\text{decimal}]$$

It will be calculated for the baseline and each post-baseline assessment using the SpO_2 (oxygen saturation) value and the FiO_2 (fraction of inspired oxygen) value collected or derived on the VS and OXYGEN or VENTUSE eCRF pages, respectively. Details on these variables and visit windows are provided in Section 3.2.6 and Section 4.1, respectively.

3.1.16 Time to clinical improvement of at least 2 points (from randomization) on a 9-point category ordinal scale through Day 28

This is defined as the time (in days) from randomization to the date of first demonstrated clinical improvement of at least 2 points (i.e., a decline of two points) on the following 9-point category ordinal scale through Day 28:

0. * Uninfected, no clinical or virological evidence of infection
1. Ambulatory, no limitation of activities
2. Ambulatory, limitation of activities
3. Hospitalized – mild disease, no oxygen therapy
4. Hospitalized – mild disease, oxygen by mask or nasal prongs
5. Hospitalized – severe disease, non-invasive ventilation or high flow oxygen
6. Hospitalised – severe disease, intubation and mechanical ventilation
7. Hospitalized – severe disease, ventilation and additional organ support, such as pressors, renal replacement therapy, extracorporeal membrane oxygenation
8. Death

*Score of zero on 9-point category ordinal scale will not be evaluated in this study.

This information will be collected in the OSCI pages in the eCRF as per the SoA in the CSP.

Baseline ordinal scale score is defined as the result obtained on the date of randomization (Day 1) only.

If a subject does not have an event (i.e., does not demonstrate clinical improvement of at least 2 points) on or before Day 28 and does not withdraw or become lost to follow up from the study on or prior to Day 28, the data will be censored at Day 28. If a subject does not have an event but withdraws from the study or is lost to follow up on or prior to Day 28, the data will be censored at the last date known that the subject has not demonstrated clinical improvement of at least 2 points up to Day 28.

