4.3.2.14 Relative change from baseline in oxygenation index

Summary statistics (n, mean, median, SD, minimum, and maximum) and the percent change from baseline to each scheduled study assessment will be presented by treatment group.

Box plots of absolute value over time and a line graph of mean change (and SD) from baseline to each scheduled study assessment may be presented for each treatment group.

A by-subject listing will also be presented.

4.3.2.15 Time to clinical improvement of at least 2 points (from randomization) on a 9-point category ordinal scale through Day 28

Time from randomization to the date of first demonstrated clinical improvement of at least 2 points on a 9-point category ordinal scale through Day 28 will be portrayed using the KM method by treatment group.

Alongside summary statistics, a KM plot of the cumulative improvement rate over time will be presented by treatment group.

The HR and its 90% CI will be estimated from a stratified Cox Proportional Hazards model (with ties = Efron), stratified by age (<65 vs ≥65 years) and comorbidities (present vs absent).

The CI will be calculated using a profile likelihood approach. Summary statistics will include the lower and upper quartile and median time to clinical improvement with the 90% CI.

The method for handling subjects that withdraw or are lost to follow up or die is detailed in Section 3.1.16.

In addition to the above, for each treatment group, ordinal scale scores will be presented by day and the change in the score from baseline to each post-baseline assessment will be summarized.

Additional sensitivity analyses may be performed as appropriate.

Time to clinical improvement of at least 2 points (from randomization) on a 9-point category ordinal scale, live discharge from hospital, or considered fit for discharge, whichever comes first) through

Time from randomization to the date of first demonstrated clinical improvement of at least 2 points on a 9-point category ordinal scale, live discharge from hospital, or considered fit for discharge, whichever comes first, through Day 28 will be portrayed using the KM method by treatment group.

Alongside summary statistics, a KM plot of the cumulative improvement rate over time will be presented by treatment group.

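### The Cox models for improvement, recovery and SpO2 >94% carry no baseline severity term, unlike the primary model; adding one protects the hazard ratio against chance imbalance at almost no cost

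*SAP*

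**What the plan says.** **Model.** SAP 4.3.2.15, for time to 2-point improvement: "The HR and its 90% CI will be estimated from a stratified Cox Proportional Hazards model (with ties = Efron), stratified by age", with comorbidities as the second factor. The same model is set for the composite-improvement and recovery versions in that section and for time to SpO2 >94% on room air in 4.3.2.16. No covariate is named. Each analysis allows further sensitivity analyses but does not specify any.

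**Events.** SAP 3.1.16 counts a drop of two points from the subject's own starting score, and fixes that start: "Baseline ordinal scale score is defined as the result obtained on the date of randomization (Day 1) only". The composite (3.1.16.1) is met by that drop, live discharge, or a score of 0 to 2. Recovery (3.1.16.2) and SpO2 >94% (3.1.17) are fixed targets, and subjects already above the SpO2 threshold on room air at baseline are left out of that analysis.

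**Severity elsewhere.** Randomization is stratified by age and comorbidities only (Protocol 4.1, 9.1). The primary logistic model includes baseline respiratory failure (Protocol 9.6.2; SAP 4.3.1.1). The analysis of time to respiratory failure or death excludes subjects who have it at baseline (SAP 3.1.8).

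**The concern.** Starting severity can vary. Inclusion criterion 4 admits subjects with low saturation on room air (score 3) or on supplemental oxygen (score 4 or higher). Exclusion criterion 1 removes respiratory failure only where swallowing is impeded or mechanical ventilation is likely within 24 hours, so score 5 can enter. With 62 subjects randomized (SAP 1.3), neither the design nor these models holds the severity mix equal between arms.

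Two consequences follow if severity is prognostic. A chance difference in mix moves the HR. And if the drug works, omitting the factor pulls the HR toward 1 relative to the HR among subjects of like severity, with some loss of power. The plan already accepts that severity matters for the primary endpoint and for time to respiratory failure or death. It gives no reason for treating these four analyses differently.

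**Working it through.** **1. The plan's own figure.** Protocol 9.2 covers the primary endpoint only: "it assumed that the proportion of subjects who are alive and free of respiratory failure at Day 28 is 70% under BSC". The target for Arm 1 is 20 points higher, at 90%. With 30 per arm the standard error (SE) is sqrt(0.7×0.3/30 + 0.9×0.1/30) = sqrt(0.007 + 0.003) = 0.10.
- Half-width: 1.645 × 0.10 = 16.45%. The plan says "the half-width of the 2-sided 90% confidence interval for the observed treatment difference is 16.4% using unpooled estimate for variance".
- Power: Phi(0.20/0.10 − 1.645) = Phi(0.355) = 63.9%. The plan says "It has approximately 64% power, with a 2-sided type I error of 0.1, to detect a difference of 20% between the 2 arms".

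Both reproduce, and neither is affected by this point. No event count, HR or power is stated for any of the four Cox endpoints.

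**2. Where the starting score enters the event.**

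| Start | 2-point event | Composite event, by score | Recovery, SpO2 >94% |
|---|---|---|---|
| 3 | reach 1 (no limitation) | reach 2 | same target for all |
| 4 | reach 2 (ambulatory) | reach 2 | same target for all |
| 5 | reach 3 (in hospital, off oxygen) | reach 3 | same target for all |

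The score therefore changes the event for the 2-point endpoint and, through that component, for the composite. For recovery and SpO2 >94%, severity can only be prognostic.

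**3. Chance imbalance.** Hypergeometric, 31 per arm. The prevalence of the worse category is assumed.

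| In worse category | SD of between-arm difference | P(difference of at least 20 points) |
|---|---|---|
| 12 of 62 (about 20%) | 10.1 points | 2.2% |
| 19 of 62 (about 30%) | 11.8 points | 9.7% |
| 25 of 62 (about 40%) | 12.6 points | 12.0% |

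**4. Simulation.** From the documents: N=62, 1:1 within four age-by-comorbidity strata, censoring at Day 28, stratified Cox, two-sided alpha 0.10. Assumed: exponential times with hazard 0.12 per day, scaled by 1, 0.8, 0.7 and 0.55 across the strata; 20% or 40% in the worse category; event HR of 0.7, 0.5 or 0.3 for that category; no deaths or dropout. These give 47 to 58 events on average. Each scenario has 1,500 trials, so the simulation SE of a power is at most sqrt(0.25/1500) = 1.3 points. The unadjusted HR in the table is the large-sample value. The last column is the multiplier on the HR when Arm 1 has 20 points more subjects in the worse category. Pairs are for 20% / 40% prevalence.

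| Conditional HR | Severity HR | Unadjusted HR | Rejection %, unadjusted | Rejection %, adjusted | Multiplier, unadjusted; adjusted |
|---|---|---|---|---|---|
| 2.0 | 0.7 | 1.982 / 1.973 | 79.7 / 78.5 | 80.2 / 79.9 | 0.92 / 0.94; 0.99 / 1.01 |
| 2.0 | 0.5 | 1.926 / 1.897 | 75.9 / 71.1 | 79.5 / 75.7 | 0.86 / 0.88; 1.00 / 1.01 |
| 2.0 | 0.3 | 1.781 / 1.762 | 68.0 / 63.0 | 76.9 / 74.9 | 0.79 / 0.81; 1.01 / 1.02 |
| 1.5 | 0.7 | 1.490 / 1.479 | 41.8 / 39.2 | 42.5 / 40.1 | 0.92 / 0.94; 0.98 / 1.01 |
| 1.5 | 0.5 | 1.465 / 1.456 | 38.9 / 37.3 | 42.9 / 41.7 | 0.88 / 0.89; 1.02 / 1.02 |
| 1.5 | 0.3 | 1.399 / 1.395 | 33.7 / 30.5 | 38.9 / 39.4 | 0.78 / 0.82; 0.99 / 1.04 |
| 1.0 | 0.7 | 0.999 / 0.999 | 11.3 / 10.5 | 11.3 / 11.1 | 0.91 / 0.92; 0.99 / 0.99 |
| 1.0 | 0.5 | 1.005 / 0.997 | 11.1 / 10.1 | 11.1 / 9.5 | 0.86 / 0.87; 0.99 / 1.00 |
| 1.0 | 0.3 | 1.012 / 0.993 | 10.5 / 9.7 | 10.9 / 10.0 | 0.79 / 0.79; 1.01 / 0.98 |

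At a conditional HR of 2.0 the power loss runs from 80.2 − 79.7 = 0.5 to 74.9 − 63.0 = 11.9 points, and the adjusted median estimate is 2.01 to 2.03. At HR 1.0 neither model shows distortion, and both reject at about the nominal 10%.

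**The case against.** The strongest case against rests on five points.

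- **The planned model is not in error.** An HR that does not condition on severity is a legitimate quantity, and type I error holds. This stands: a reader might infer that the planned HR is biased or invalid, and it is not. But that HR already conditions on two prognostic factors, so conditioning on a third is no change of principle.
- **The confidence interval already allows for chance imbalance.** With 47 to 58 events, SE(log HR) is about 2/sqrt(events) = 0.29 to 0.26, so the 90% interval spans a factor of about 1.62 to 1.54 each way. A 20-point imbalance moves the HR by less than that. This stands for coverage over repeated trials. It does not help the reader of one trial whose arms visibly differ in severity.
- **Strength and direction are assumed.** This stands. For the 2-point event, a score-5 subject can qualify in hospital while a score-4 subject must become ambulatory, so the documents do not show that score 5 slows the event. At a severity HR of 0.7 the gain is negligible. A covariate handles either direction.
- **These are secondary or exploratory analyses with no formal testing** (Protocol 9.1). This stands as to power. Estimation is then the aim, and the HR with its interval is the result.
- **Imbalance would be visible, and sensitivity analyses are allowed.** Baseline respiratory failure and oxygen support are summarized by arm (SAP 3.5.1, 4.2.3). But no covariate is named, and one chosen after open-label results are known carries little weight.

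A reader might also infer that the starting score defines the event in all four models. SAP 3.1.16.2 and 3.1.17 do not support that: recovery and SpO2 >94% are the same target for everyone. Nor does a two-level covariate make the 2-point event uniform, because scores 3 and 4 still have different targets.

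**Conclusion.** The point holds as a gap in precision and consistency, not as an invalid analysis. Four Cox models omit baseline severity, randomization does not balance it, and the primary model adjusts for it. The 2-point endpoint is most exposed because its event depends on the starting score; the composite is exposed through that component, and the other two only if severity is prognostic.

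Under the assumed inputs (20-40% in the worse category, severity HR 0.3-0.7, N=62), a conditional HR of 2.0 becomes 1.76-1.98, and one of 1.5 becomes 1.40-1.49. Power falls by about 0-12 points. A 20-point imbalance has probability 2-12% and multiplies the unadjusted HR by 0.78-0.94, against 0.98-1.04 when adjusted. A reader might take these as predictions for this trial. They are not, because the documents give neither the severity mix nor its effect on these events.

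**What to change.** Before database lock, add baseline respiratory failure (with vs without), as in the primary logistic model, as a covariate in the Cox models of SAP 4.3.2.15 (all three versions) and 4.3.2.16. Baseline ordinal score (4 or below vs 5 or above) would serve almost equally. The two differ only at the margin, since high-flow oxygen below the protocol's flow or oxygen-fraction threshold scores 5 without meeting the failure definition. Choose one in advance. Enter it as a covariate rather than a further stratum, because 62 subjects already span four strata. Keep the current model as a named sensitivity analysis.

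Use the SAP's Day 1 baseline for the covariate and say how a missing Day 1 value is handled. Falling back to a score from before randomization would conflict with the Day-1-only rule in SAP 3.1.16 and 4.1. It should not be adopted unless the same rule also sets the baseline that defines the event.

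Cost: a sentence or two of SAP text and one term already derived for the primary analysis.

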4.3.2.16 Time to SpO₂ > 94% on room air

Time from randomization to SpO₂ > 94% on room air through Day 28 will be portrayed using the KM method by treatment group.

Alongside summary statistics, a KM plot of the cumulative SpO₂ > 94% rate over time will be presented by treatment group.

The HR and its 90% CI will be estimated from a stratified Cox Proportional Hazards model (with ties = Efron), stratified by age (<65 vs ≥65 years) and comorbidities (present vs absent). The CI will be calculated using a profile likelihood approach. Summary statistics will include the lower and upper quartile and median time to clinical improvement with the 90% CI.

The method for handling subjects that withdraw or are lost to follow up or die is detailed in Section 3.1.17.

Additional sensitivity analyses may be performed as appropriate.

4.4 Analysis of safety

This section describes safety analyses to be conducted. All of the analyses in this section will be based on the safety population and will be performed for all safety variables specified below. All analyses of safety data will employ descriptive statistics. Formal statistical analysis (with generation of a p-value) will not be performed for these endpoints.

4.4.1 Adverse events

Verbatim descriptions of AEs will be mapped per version 23.0 of the MedDRA thesaurus terms and graded per National Cancer Institute (NCI) CTCAE, v5.0 or higher. Unless stated otherwise, only treatment-emergent adverse events (TEAEs) will be presented in the summaries. For acalabrutinib + BSC subjects, TEAEs are AEs starting or ongoing AEs worsening after the first dose of study treatment and AEs with start date up to the last dose of study treatment plus 28 (±3) days; for BSC only subjects, TEAEs are AEs starting or ongoing AEs worsening after date of randomization and AEs with start date up to 38 (± 3) days after randomization. In the case a subject's actual treatment received is different than their randomized treatment, TEAEs are AEs starting on or after the date of randomization up to the later of 38 (± 3) days after randomization or the last dose of study treatment plus 28 (±3) days. When programmatically assigning the AEs as treatment emergent, the upper window will be used.

The following summaries will be provided:

- A summary of the number and percentage of subjects reporting any TEAE, TEAEs with outcome of death, at least one TEAE of CTCAE grade 3 or higher, at least one serious TEAE, at least one TEAE possibly related to study drug, and at least one TEAE leading to discontinuation of study drug by treatment group.
- A summary of the number of TEAEs, TEAEs with outcome of deaths, TEAEs with CTCAE grade 3 or higher, serious TEAEs, TEAEs possibly related to study drug, and TEAEs leading to discontinuation of study drug by treatment group.
- A summary of the number and percentage of subjects reporting a TEAE by treatment group, SOC and PT.
- A summary of the number and percentage of subjects reporting the most common TEAEs (occurring in at least 5% of overall subjects) by treatment group, SOC and PT.
- A summary of the number and percentage of subjects reporting a TEAE by treatment group, CTCAE grade, SOC and PT. This will include a subset of grade 3 or higher.
- A summary of the number and percentage of subjects reporting a TEAE possibly related to study drug by SOC and PT.
- A summary of the number and percentage of subjects reporting a TEAE leading to discontinuation of study drug by SOC and PT.

For the most common TEAEs, all events that occur in at least 5% of subjects overall will be summarized by preferred term, by decreasing frequency. This cut-off may be modified after review of the data. When applying a cut-off (e.g., 5%), the raw percentage should be compared to the cut-off, no rounding should be applied first (i.e., an AE with frequency 4.9% will not appear if the cut-off is 5%).

The following by-subject listings will be provided:

- A listing of all AEs (including non-treatment-emergent events and any collected but are not, by definition, AEs since they are related to disease under study), by treatment group, and including center, E-code, AE (SOC, PT, verbatim term), date of onset, date of resolution, duration, CTCAE grade, seriousness, action taken, outcome, relationship to study treatment and time from last dose to start of AE.

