8.6.4 Adverse Event Data Collection

The following variables will be collected for each AE:

- AE diagnosis/description
- The date when the AE started and stopped
- Maximum Common Terminology Criteria for Adverse Events (CTCAE) grade
- Whether the AE is serious or not
- Investigator causality rating against the investigational product (yes or no)
- Action taken regarding investigational product
- Administration of treatment for the AE
- Outcome

In addition, the following variables will be collected for SAEs:

- Date AE met criteria for SAE
- Date Investigator became aware of SAE
- Seriousness criteria
- Date of hospitalisation
- Date of discharge
- Probable cause of death
- Date of death
- Autopsy performed
- Causality assessment in relation to study procedure(s)
- Causality assessment to other medications
- Description of SAE

The grading scales found in the revised NCI CTCAE Version 5.0 will be utilized for all events with an assigned CTCAE grading. For those events without assigned CTCAE grades, the recommendation in the CTCAE criteria that converts mild, moderate, and severe events into CTCAE grades should be used. A copy of the CTCAE Version 5.0 can be downloaded from the Cancer Therapy Evaluation Program website

(https://ctep.cancer.gov/protocolDevelopment/electronic_applications/docs/CTCAE_v5_Quic k_Reference_8.5x11.pdf).

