9.6.1 Safety Analyses

Safety assessments will consist of monitoring and recording AEs, SAEs and AEs leading to discontinuation of study treatment; measurements of protocol-specified hematology, clinical chemistry, and other laboratory variables; measurement of protocol-specified vital signs; and other protocol-specified tests that are deemed critical to the safety evaluation of the study treatment. All safety analyses will be performed on the safety analysis set as defined in Section 9.3.

Verbatim descriptions of AEs will be mapped per the most recent version of Medical Dictionary for Regulatory Activities (MedDRA) thesaurus terms and graded per National Cancer Institute (NCI) CTCAE, v5.0 or higher. Extent of exposure to study treatment, all AEs, SAEs, any AEs leading to study treatment discontinuation, and study treatment related AEs will be summarized. The frequency of AEs will be summarized by system organ class and preferred terms per MedDRA by the worst reported NCI CTCAE grade. TEAEs will be summarized, unless otherwise specified. In this study, for Arm 1 (acalabrutinib + BSC), TEAEs are defined as AEs starting or ongoing AEs worsening after the first dose of study treatment and AEs with start date up to the last dose of study treatment plus 28 (\pm 3) days; for Arm 2 (BSC only), TEAEs are defined as AEs starting or ongoing AEs worsening after the date of randomization and AEs with start date up to 38 (\pm 3) days from randomization.

Laboratory abnormalities will be defined based on laboratory normal ranges (universal normal ranges, if central laboratory). Selected laboratory parameters may be analysed with shift tables and summaries of changes from baseline to worst post-treatment value.

Vital sign and all other safety assessments will be tabulated and summarized.

Full details of AE, laboratory assessments, vital sign assessments and all other safety assessments will be provided in the SAP.

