3.2.1 Adverse events

After the signing of the ICF, all SAEs must be reported. After the first dose of study treatment, all AEs/SAEs, irrespective of attribution of causality, must be reported. AE reporting, irrespective of seriousness, ends 28 (± 3) days after the last dose of study treatments(s) for those on acalabrutinib + BSC (Arm 1) and 38 (± 3) days from randomization for those on BSC only (Arm 2).

The following are NOT considered an AE:

- **Pre-existing condition that has not worsened:** A pre-existing condition (documented on the medical history eCRF) is not considered an AE unless the severity, frequency, or character of the event worsens during the study period.
- **Diagnostic testing and procedures:** Testing and procedures should not be reported as AEs or SAEs, but rather the cause for the test or procedure should be reported. If a test or procedure is done to rule out a diagnosis, the sign or symptom leading to the test/procedure should be the event term, and the event term should only be updated to the diagnosis if/when the diagnosis is confirmed. Testing and procedures performed solely as screening measures (e.g., routine screening mammography or colonoscopy) should not be reported as AEs or SAEs.
- **Abnormal laboratory results:** Abnormal laboratory results are not AEs unless they are clinically significant. For example, a clinically significant laboratory result is one that requires treatment (for example a blood transfusion for low haemoglobin) or requires a change in study drug (e.g., lowering the dose or withholding study drug while the laboratory finding resolves or stabilizes).
- **Progression of underlying disease:** Progression of underlying disease unequivocally related to COVID-19 pneumonia (such as worsening of respiratory status or complications associated with pneumonia) will not be reported as an AE if it is clearly consistent with the suspected progression of the underlying disease. Clinical symptoms of progression may be reported as AEs if the symptoms cannot be determined as exclusively due to the progression of the underlying disease, or if

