No imputation of values for missing data will be performed except for missing or partial start and end dates for AEs and concomitant medication(CM) (Table 6). If the data cut-off/snapshot date or the subject’s date of death is prior to the date imputed based on the rules outlined below, then the earliest of these dates will be imputed.

Table 6 Imputation rules for missing or partial AE on concomitant medication dates

Form		Imputation	
		Acalabrutinib + BSC	BSC alone
	Start date		
	Missing		

AE and CM	AE/CM ended before first dose date/ randomization date	Impute 1 st January with year being the same year as CM/AE end date	
	AE/CM ended after first dose date/ randomization date	Impute date of first dose	Impute date of randomization
	Partial		
AE and CM	Missing day	Impute 1 st of the month unless AE/CM start month is the same month as the first dose, then impute date of first dose. Check start date is prior to end date.	Impute 1 st of the month unless AE/CM start month is the same month as randomization, then impute date of randomization. Check start date is prior to end date.
	Missing day and month	Impute 1 st January unless AE/CM start year is the same year as the first dose, then impute date of first dose. Check start date is prior to end date. If end date is now prior to start date, impute 1 st January as the start day and month.	Impute 1 st January unless AE/CM start year is the same year as randomization, then impute date of randomization. Check start date is prior to end date. If end date is now prior to start date, impute 1 st January as the start day and month.
	End date		
	Missing		
AE and CM	CM flag ongoing takes any value (yes, no or missing) and CM start date is prior, on or after first dose date/ randomization AE stop date missing	Impute min (date of death, data cut-off/snapshot date)	
	Partial		
CM	Missing day	Impute the last day of the month unless month is the same as month of last dose, then impute date of last dose.	Impute the last day of the month unless month is the same as month of randomization date + 10 days, then impute randomization date + 10 days.

	Missing day and month	Impute date of last dose + 28 days + 3 days	Impute date of randomization + 38 days + 3 days
--	-----------------------	---	---

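### The TEAE rule for BSC counts only AEs starting after the randomization date, so it excludes Day 1 onsets and AEs whose missing start is imputed to that date

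*SAP*

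**What the plan says.** **Start of the window, BSC.** SAP 4.4.1: "for BSC only subjects, TEAEs are AEs starting or ongoing AEs worsening after date of randomization". Protocol 9.6.1 agrees: "for Arm 2 (BSC only), TEAEs are defined as AEs starting or ongoing AEs worsening after the date of randomization".

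**Start of the window, acalabrutinib + BSC.** SAP 4.4.1: "TEAEs are AEs starting or ongoing AEs worsening after the first dose of study treatment". The anchor is an event, not a calendar date. Protocol 6.1.1 expects that dose on Day 1, within 6 hours of randomization.

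**Subjects whose actual treatment differs from the randomized arm.** The same SAP paragraph uses an inclusive rule: "TEAEs are AEs starting on or after the date of randomization up to the later of 38" days (±3) after randomization or 28 (±3) days after the last dose.

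**Imputation.** SAP 4.1, Table 6, sets a BSC start date to the randomization date in three cases:
- the start is wholly missing and the AE ended after randomization;
- only the day is missing and the month is that of randomization ("unless AE/CM start month is the same month as randomization, then impute date of randomization");
- day and month are missing and the year is that of randomization, unless that would fall after the end date, when 1 January is used.

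For acalabrutinib the table is parallel, with the first-dose date as anchor. Protocol 9.5 describes the date imputation as conservative.

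**Data collected.** Protocol 8.6.4 lists "The date when the AE started and stopped" and no onset time.

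**Start of reporting.** SAP 3.2.1: "After the first dose of study treatment, all AEs/SAEs, irrespective of attribution of causality, must be reported". Protocol 8.6.2 starts it at randomization for both arms, with SAEs only between consent and randomization.

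**The concern.** AE summaries show only TEAEs unless stated otherwise (SAP 4.4.1), and SAP 3.2 names safety as a primary endpoint. The start rule therefore decides which AEs enter the main safety display.

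Three things look wrong:
- The strict rule removes BSC Day 1 onsets. Under protocol 8.6.2 non-serious AEs are reported only after randomization, so a non-serious Day 1 AE in a BSC subject is by the collection rule an on-study event.
- Imputation and TEAE rule work against each other. Conservative imputation is meant to keep an AE of uncertain onset in the tables. Here it gives the AE the one on-study date that the TEAE rule rejects.
- The BSC safety group mixes two rules. A subject randomized to acalabrutinib but never dosed is summarized as BSC (SAP 2.1.3) and counted *on or after* randomization, while every other BSC subject is counted *after* it. The same Day 1 event could be classed differently within one column.

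**Working it through.** The plan states no figure on this point, so the check applies the two rules to test cases.

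**Inputs.** Day 1 is the randomization date (SAP 4.1). The upper window is used (SAP 4.4.1), so the BSC window closes 38 + 3 = 41 days after randomization, on Day 42. Test subject: randomized on 15 July 2020 (a hypothetical date).

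**Rule.** Impute the start by Table 6. Then call the AE a TEAE if anchor < start ≤ anchor + 41 (*after*), or if anchor ≤ start ≤ anchor + 41 (*on or after*).

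| Test AE in a BSC subject | Start used | *after* | *on or after* |
|---|---|---|---|
| Complete date, Day 1 | 15 July | no | yes |
| Complete date, Day 2 | 16 July | yes | yes |
| Start wholly missing, ended 25 July | 15 July | no | yes |
| Start wholly missing, ended 10 July | 1 January | no | no |
| July, day missing, ended 25 July | 15 July | no | yes |
| August, day missing, ended 9 August | 1 August | yes | yes |
| 2020, day and month missing, ended 9 August | 15 July | no | yes |

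Four of the seven are lost under *after* and recovered under *on or after*. The AE that ended before randomization stays out under both, as it should. The AE with only the day missing in a later month stays in under both. An AE that starts on Day 1 and worsens on a later day still counts, through the worsening part of the definition.

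**Year-only dates.** The SAP amendment history shows that the number randomized was known on 8 September 2020, and SAP 1.3 says that recruitment was then complete. 8 September + 41 days = 19 October, so every BSC window closes within 2020. A BSC AE with onset in the window and only the year recorded therefore always shares the randomization year and is lost.

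**The same cases in acalabrutinib-treated subjects.** Take the first dose on 15 July and the last on Day 10, so that the window closes 9 + 31 = 40 days after the anchor date. On dates alone, the results in both columns are the same as for BSC. A Day 1 AE after the dose counts only if the program can place it after the dose, or if it treats *after the first dose* as including the dosing date.

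**Length of window.** BSC has 41 calendar days under *after* (Days 2 to 42) and 42 under *on or after*. This shows where the boundary lies; it does not estimate the AEs lost.

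**The case against.** A reader might infer that events are lost from the control arm only, so that acalabrutinib looks relatively worse. The documents do not establish this. Both definitions say *after*, Table 6 treats the arms in parallel, and protocol 8.6.4 lists only dates. A strict date comparison drops Day 1 and imputed AEs among acalabrutinib-treated subjects too. What remains is a difference in wording: a post-dose Day 1 AE can qualify under the acalabrutinib definition, while no Day 1 onset can qualify as such under the BSC one.

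A reader might also infer that imputed AEs in general drop out. Only those imputed to the anchor date do.

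On consequence, the objection is largely right. Safety is one of the primary endpoints but is analysed descriptively, without p-values (SAP 4.4), and the documents do not call it co-primary or plan a formal safety comparison. The listing of all AEs includes non-treatment-emergent events, SAEs are listed by subject, and total deaths are not restricted to TEAEs (SAP 4.4.1 and 4.4.1.1). The documents do not show that any subject with mismatched treatment exists, or that partial dates are common. SAP 3.2.1 misstates the start of reporting, but the protocol governs collection, so that sentence alone changes no count.

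The rule cannot be set aside as loose phrasing, however. The same SAP paragraph uses both *after* and *on or after*, and a programmer would take them as two different comparisons.

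**Conclusion.** The point holds in limited form. As written, the BSC rule excludes Day 1 onsets that do not later worsen, and it excludes AEs whose start Table 6 sets to the randomization date. That defeats the purpose of the imputation, and the SAP is inconsistent within the BSC safety group.

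The effect is confined to the TEAE tables. Its direction is open: it is one-sided if the acalabrutinib rule is programmed to include the dosing date and the BSC rule is not, and it affects both arms if both are programmed as strict date comparisons. The number of AEs affected cannot be derived, because the documents give neither the frequency of Day 1 onsets nor that of partial dates. The conclusion rests on reading *after* literally and on onset times not being collected, as protocol 8.6.4 suggests.

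**What to change.** - In SAP 4.4.1 and protocol 9.6.1, define TEAEs as AEs starting or worsening *on or after the date of randomization* for BSC and *on or after the date of first dose* for acalabrutinib-treated subjects.
- State that an AE imputed to the anchor date counts as treatment-emergent.
- Change SAP 3.2.1 so that AE reporting starts after randomization, as in protocol 8.6.2.

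The cost is a wording change and one comparison operator in the program, with no new data. The downside is that a few Day 1 events that began before randomization or before the first dose may be counted. This need not be equal in the two arms: before randomization only SAEs are reported, whereas between randomization and first dose all AEs are. The anchors also remain different, so a first dose given on a later date would still start that subject's window later than a BSC subject's.
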